4.4.2. BCVA

The number and percent of subjects with a loss in BCVA of 15 or more letters from baseline in the study eye at any follow-up study visit and by each study visit and the associated 95%

confidence intervals will be tabulated. Confidence intervals will be based on the Clopper-Pearson method.

4.4.3. Serology and Antibody

The number, proportion of participants with positive serum antibody to CNTF and the associated 95% confidence intervals will be tabulated at Baseline, Months 1, 3, and 6 post-surgery. The 95% confidence interval for the proportion will be estimated using the Clopper-Pearson method.

Geometric means, geometric standard deviations and the associated 95% confidence interval for the serum Ab titers will also be calculated. Confidence intervals will assume serum antibody titers are distributed according to a log-normal distribution.

The geometric mean fold-rise (GMFR) from baseline to Months 1, 3, and 6 post surgery and the associated 95% confidence intervals will be calculated. GMFRs will be calculated as the anti- \log_{10} of the mean of the \log_{10} transformed fold rise values. Confidence intervals will be calculated based on exponentiation of the \log_{10} transformed fold-rise values from the t-distribution.

Analyses of neutralizing antibodies to CNTF, antibodies to NTC-201.6A cells, and antibodies to DFHR will be performed using the same approach described above for the analyses of serum antibody to CNTF.

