3 STUDY ENDPOINTS

Primary Safety Endpoints

- Number and proportion of adverse events from day of surgery through 6 months post implantation
- Number and proportion of severe adverse events from day of surgery through 6 months post implantation
- Number and proportion of ocular adverse events from day of surgery through 6 months post implantation
- Number and proportion of non-ocular adverse events from day of surgery through 6 months post implantation

Secondary Safety Endpoints

- Number and proportion of participants with a loss in BCVA of 15 or more letters from baseline in the study eye using the Early Treatment Diabetic Retinopathy Study (ETDRS) distance chart
- Number and proportion of participants with at least 1 treatment-emergent serious adverse event (SAE)
- Detectable serum levels of CNTF at Months 1, 3 and 6 post-implantations of NT-501
- Number and proportion of participants with serum Ab or Nab to CNTF, Ab to NTC-201.6A cells and Ab to DFHR at Baseline and Months1, 3 and 6 post-implantation of NT-501

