1.3.7. Secondary Safety Parameters

Secondary safety endpoints are:

- Number and proportion of participants with a loss in BCVA of 15 or more letters from baseline in the study eye using the Early Treatment Diabetic Retinopathy Study (ETDRS) distance chart
- Number and proportion of participants with at least 1 treatment-emergent serious adverse event (SAE)
- Detectable serum levels of CNTF at Months 1, 3 and 6 post-implantations of NT-501
- Number and proportion of participants with serum Ab or Nab to CNTF, Ab to NTC-201.6A cells and Ab to DFHR at Baseline and Months 1, 3 and 6 post-implantation of NT-501

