3.4. Baseline Definitions

For all analyses, baseline will be defined as the most recent measurement prior to surgical implantation of the NT-501 device in the study eye. Prior to enrollment into the NTMT-02B study, all subjects previously received an implant as part of their participation in either the Phase 1/2 extension study (NTMT-01/02E) or the Phase 3 study (NTMT-03). As a result, participants' fellow eyes in the prior studies will be the study eye in the current study.

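### Every participant already carries one NT-501 implant, yet the antibody positivity endpoint does not distinguish pre-existing from new or boosted antibodies; only the group-level fold-rise is referenced to baseline.

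*SAP*

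**What the plan says.** Prior exposure is universal. SAP 3.4 states that "all subjects previously received an implant as part of their participation in either the Phase 1/2 extension study" or the Phase 3 study, and Protocol 5.2 requires Phase 3 entrants to have completed Month 24. In the same SAP section, "baseline will be defined as the most recent measurement prior to surgical implantation of the NT-501 device in the study eye". Baseline is therefore taken before the second implant but after exposure to the first. The eligibility criteria in Protocol 5.2 and 5.3 contain no antibody criterion.

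The endpoint in Protocol 3, repeated in SAP 1.3.7, is "Number and proportion of participants with serum Ab or Nab to CNTF, Ab to NTC-201.6A cells and Ab to DFHR at Baseline" and at Months 1, 3 and 6. SAP 4.4.3 implements it as a proportion at each visit ("participants with positive serum antibody to CNTF and the associated 95% confidence intervals will be tabulated at Baseline" and Months 1, 3 and 6) and adds "The 95% confidence interval for the proportion will be estimated using the Clopper-Pearson method". It also plans geometric mean titers and "The geometric mean fold-rise (GMFR) from baseline to Months 1, 3, and 6 post surgery", with confidence intervals. The other three antibody analyses "will be performed using the same approach described above for the analyses of serum antibody to CNTF".

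Neither document defines seroconversion, a treatment-emergent or boosted antibody response, or a fold-rise that marks a responder. SAP 3.8 plans no subgroup analyses, so there is no split by baseline antibody status.

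**The concern.** A second exposure raises two questions about individuals: do people who were antibody-negative before the second surgery become positive, and do the titers of people who were already positive rise? Percent positive by visit answers the first only if nobody is positive at baseline, and it does not address the second. An unchanged percentage could be read as no immune response when some participants have converted and others reverted.

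GMFR does compare each participant with their own baseline, but it averages over the cohort. In a study of about 30 people, one or two strong responses can be diluted by participants who do not change.

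Immunogenicity after bilateral implantation is part of the study's secondary objective, so a reader will look to these tables for the number of new responders.

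**Working it through.** The plan has no figure of its own to reproduce: the analysis is descriptive and no sample size was calculated.

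**Inputs.** n = 30 is the enrolment minimum (Protocol 5.1). The Clopper-Pearson interval and the log10, t-based GMFR come from SAP 4.4.3. Baseline positivity and the size of any titer rise are not in the documents, so the values below are assumptions. I also assume that all 30 give samples at both visits. That is a best case, because Protocol 5.2 allows a participant to refuse blood collection and still take part.

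**1. What the positivity table leaves open.** Let b be the number positive at Baseline and m the number positive at a later visit. The number of new converters lies between max(0, m − b) and min(m, n − b). The lower limit assumes the fewest possible reversions. In the rows below, the upper limit requires every baseline-positive participant to revert. For a net rise of 2:

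| Positive at Baseline | Positive later | Possible new converters | As a share of baseline-negatives (95% CI) |
|---|---|---|---|
| 0/30 | 2/30 | exactly 2 | 2/30 = 6.7% (0.8 to 22.1) |
| 3/30 | 5/30 | 2 to 5 | 2/27 = 7.4% (0.9 to 24.3) up to 5/27 = 18.5% (6.3 to 38.1) |
| 6/30 | 8/30 | 2 to 8 | 2/24 = 8.3% (1.0 to 27.0) up to 8/24 = 33.3% (15.6 to 55.3) |

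A flat percentage is no clearer. With 9/30 positive at both visits, new converters could number from 0/21 (0%, CI 0 to 16.1) to 9/21 (42.9%, CI 21.8 to 66.0).

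**2. What the GMFR can mask.** GMFR = 10^(mean of log10 fold-rise). If k of 30 participants rise f-fold and the rest do not change, this equals f^(k/30). The 95% CI is 10^(mean ± 2.045 × SD/√30).

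- One 64-fold rise: mean log10 = 1.806/30 = 0.0602, standard error 0.0602. GMFR 1.15, CI 0.87 to 1.53.
- Two 16-fold rises: 16^(2/30) = 1.20, CI 0.93 to 1.56.
- Three 16-fold rises: 16^(3/30) = 1.32, CI 0.96 to 1.81.
- Six 4-fold rises: 4^(6/30) = 1.32, CI 1.07 to 1.63.

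The first three intervals include 1 despite strong individual responses. The last two cases share a GMFR but describe different patterns of response.

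**The case against.** A reader might infer that carried-over antibodies cannot be separated from new ones at all. The documents do not support that. Baseline antibody is measured before the second implant, and the GMFR is a paired statistic for all four antibodies that removes stable carry-over at group level. Protocol 11.3.1 supports summary tables with individual listings, and SAP 3.10 lists all case report form data. With about 30 participants and four sampling visits, someone could reconstruct the pairs by hand. The data allow separation; what is missing is a planned summary.

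The SAP also implements the endpoint as written, in a descriptive study with no decision rule attached. That stands, and it limits how serious the point is. Listings still do not replace an analysis: without a threshold set in advance, deciding who counts as boosted becomes a judgement made after seeing the data.

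Protocol 11.3.1 further plans a count and titer of antibodies to CNTF (including neutralizing antibodies) and to the NTC-201.6A cells seen at Month 3 and persisting to Month 6. This works within participants but does not refer to baseline status, and it does not appear in SAP 4.4.3. It does not fill the gap.

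Finally, the upper bounds require all baseline-positives to revert, and nothing in the documents suggests that this is likely. If baseline positivity is zero, the ambiguity about new converters disappears.

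**Conclusion.** The point holds as a gap in the analysis definition. The design and the data collection do not need to change. Once anyone is positive at baseline, the planned percentages do not identify the number of new converters, and the only baseline-referenced summary is a group average that can mask a few strong responses.

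The size depends on baseline positivity, which is unknown. For a net rise of 2 in 30 there is no ambiguity at 0/30 positive at baseline, and the possible number of converters spans 2 to 5 at 3/30 and 2 to 8 at 6/30. These ranges assume complete pairs in 30 participants and are bounds, not predictions.

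A reader might also infer that the added table would isolate the effect of the second implant. It would not. There is no concurrent single-implant control, so a new or boosted response after the second surgery could reflect continuing exposure to the first implant.

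**What to change.** In SAP 4.4.3, for each of the four antibodies:

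- Add a 2x2 table of Baseline by visit status at Months 1, 3 and 6, restricted to participants with paired samples, and state that number.
- Report treatment-emergent positivity with baseline-negatives as the denominator and a Clopper-Pearson 95% CI, the method the SAP already uses.
- List baseline-positive participants with their individual fold-rises. Report a count of boosted participants only if a fold-rise threshold is fixed before database lock. The documents give no assay precision from which to set one.
- State how negative or below-limit titers enter the fold-rise, since the SAP gives no rule.
- Keep the visit percentages and GMFR as supporting output.
- State that, without a concurrent single-implant control, a new or boosted response cannot be attributed with certainty to the second implant.

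The cost is SAP text and one table shell and listing per antibody, plus input from the laboratory if a boost threshold is wanted. No extra visits or samples are needed. The drawback is small denominators within each baseline stratum, especially among baseline-positives: 0 of 6 boosted would have a 95% CI of 0 to 45.9%.

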4.4.4. Ophthalmic Exam

The ophthalmic exam consists of an external exam of the eye and adnexa, screening for eyelid and pupil responsiveness, slit lamp biomicroscopy, indirect ophthalmoscopy and intraocular pressure. Ophthalmic exams of study and fellow eyes will occur at baseline, Months 1, 3, and 6 post-surgery; additional exams of study eyes only will occur 1 day and 1 week post-surgery.

Ophthalmic exam results will be provided in data listings.

4.5. Evaluation of Additional Safety Assessments

Additional safety assessments will be conducted using the Safety population.

4.5.1. Study Drug Exposure

Study drug exposure will be calculated as the number of subjects who received the NT-501 implant in their study eye.

The number and percent of subjects who had an implant removed prior to the Month 6 visit will be calculated. By-subject listings will be generated for these subjects noting which implant(s),

either from the current study or received during previous studies, was removed and the reason for removal.

4.5.2. Laboratory Data

Clinical laboratory values will be expressed in reported units or SI units. Serum chemistry, hematology, and urinalysis are performed only at baseline.

The actual value will be summarized for each clinical laboratory parameter. In the event of repeat values, the last non-missing value per study day/time will be used.

All laboratory data will be provided in data listings.

A subset listing will be presented for all abnormal laboratory values.

4.5.3. Vital Signs and Medical Examination

Vital signs are collected at baseline only. Actual values will be summarized using descriptive statistics and measurements will be presented for each subject in a data listing.

Medical examinations will occur at screening or baseline only and are standard for any surgical procedure. All findings will be presented in a data listing.

4.5.4. Concomitant Medications and Non-study Procedures

Concomitant medications will be coded using the WHO Drug Dictionary and Non-study procedures. Concomitant medications will be tabulated by anatomic therapeutic class (ATC) and preferred term. Non-study procedures will be tabulated by SOC and preferred term.

Any medications that did not end prior to date of surgical implantation will be included. If an end date is missing or the medication is ongoing, the medication will be included.

The use of concomitant medications will be included in a by-subject data listing.

5. CHANGES TO PLANNED ANALYSES

As of this date, there have been no changes between the protocol-defined statistical analyses and those presented in this statistical analysis plan.

